4.6.1 Definitions of Study Assessments

4.6.1.1 Clinical Evaluations

- **Demographic Data:** date of birth and sex will be collected; the patient's race/ethnicity data will also be entered. At a minimum, year of birth and sex will be retrieved.
- **Vital Signs:** will include measurements of pulse, temperature, respiration rate, and systolic and diastolic blood pressure while the patient is in a seated position. Vital signs should be obtained before injection of lampalizumab.
- **Physical Examination:** should include an evaluation of the head, eyes, ears, nose, throat, and cranial nerves. If any abnormalities are noted during the study, the patient may be referred to another physician with specialty expertise. The investigator should use his or her clinical judgment for appropriate treatment and/or medical referral. New or worsened clinically significant abnormalities should be recorded as adverse events on the Adverse Event eCRF. Height and weight will be collected for patients enrolling from CFD4870g study.
- **Medical History (including surgeries, procedures and ocular therapy history):** the patient's data will be retrieved from the CFD4870g and GX29455 databases.

4.6.1.2 Ocular Assessments

- BCVA on ETDRS chart at a starting distance of 4 meters (perform prior to dilating eyes; see [Appendix 3](#))
- Pre-injection IOP measurement for both eyes (perform prior to dilating eyes; the method used for this assessment must remain consistent throughout the study)
- Slit-lamp examination (see definition of ocular inflammation see Section [5.1.3](#); for inflammation grading scales, see [Appendix 2](#))
- Dilated binocular indirect ophthalmoscopy
- Finger-counting test, or hand motion, or light perception tests performed by the investigator within 15 minutes post-injection for the study eye only
- IOP measurement at 60 (± 10) minutes post-injection for the study eye only; if IOP increased ≥ 10 mmHg from pre-injection, the patient will remain in the clinic and will be treated according to the investigator's clinical judgment prior to the patient's discharge; if applicable, an Adverse Event eCRF page will be completed (see Section [5.2.2](#)). The method of IOP measurement used for a patient must remain consistent throughout the study

Note: if the study eye is treated with a ranibizumab injection during the same visit as the study treatment with lampalizumab, the treatment with ranibizumab has to be performed first. Please measure and record the post-ranibizumab treatment IOP value on the appropriate eCRF.

4.6.1.3 Ocular Imaging

An independent review of digital color fundus photographs, fluorescein angiograms, FAF, NI, and SD-OCT images (including exploratory anatomic biomarker studies) will be performed at a central reading center to provide an objective analysis of these assessments. The central reading center evaluation will be performed by graders and retinal specialists experienced in the conduct of AMD clinical trials.

The central reading center will provide sites with a study manual and training material for specified study ocular images. Before any study images are obtained, site personnel, test images, systems and software (where applicable) will be certified/validated by the reading center as specified in the study manual. “Grandfathering” certifications for personnel and equipment from CFD4870g or GX29455 will be allowed as per reading center guidelines. All ocular images will be obtained by trained site personnel at the study sites and forwarded to the central reading center for independent analysis and/or storage.

Ocular images obtained include the following:

- Stereoscopic, digital color fundus photographs of both eyes (see [Appendix 4](#))
- Fluorescein angiograms of both eyes (perform after laboratory samples are obtained; see [Appendix 5](#))
- FAF, SD-OCT, and NI images of both eyes;(see [Appendix 6](#), [Appendix 7](#), and [Appendix 8](#), respectively)

Note: after enrollment, if a patient misses a study visit during which ocular images were scheduled to be taken (see [Appendix 1-A](#) through [Appendix 1-E](#)), the images should be obtained at the next scheduled visit.

Additional details on obtaining these images are included in the central reading center manual.

4.6.1.4 Laboratory Assessments

At the scheduled visit, specimens should be collected prior to study eye treatment and FA assessments (if applicable). Fasting is not required prior to specimen collection. All specimens will be forwarded to the central laboratory for processing. The central laboratory will either perform the analysis or forward to Genentech for analysis. Instructions for obtaining, processing, storing, and shipping of all specimens are provided in the Laboratory Manual. Laboratory supply kits will be provided to the sites by the central laboratory. See [Appendix 1-A](#) through [Appendix 1-E](#) for the collection timepoints of samples.

The following assessments will be performed:

- Hematology: hemoglobin, hematocrit, quantitative platelet count, RBC, WBC, and differentials including neutrophils, bands, lymphocytes, basophils, eosinophils, and monocytes (absolute and percent)
- Coagulation: aPTT and PT
- Serum chemistry: sodium, potassium, chloride, bicarbonate, glucose, blood urea nitrogen (BUN), creatinine, calcium, phosphorus, total and direct bilirubin, total protein, albumin, AST, ALT, LDH, alkaline phosphatase, and uric acid
- Urinalysis: specific gravity, pH, blood, protein, ketones, glucose, bilirubin, urobilinogen, microscopic examination (if any of the preceding urinalysis tests, other than glucose and ketones, are abnormal)
- Serum sample to measure anti-lampalizumab antibodies (ATA) and drug concentration at ATA sample timepoint collections

Optional Clinical Genotyping Samples:

- An optional, single, whole-blood sample will be collected for genotyping analysis at any time during the study from German study site patients; of note, blood samples for genotyping analysis from the U.S. study site patients were collected previously in Study CFD4870g and Study GX29455. The genotyping samples will be used to evaluate relationships between genetic polymorphisms associated with AMD, baseline disease characteristics, and response to administration of lampalizumab.

4.6.2 Screening and Pretreatment Assessments

After a patient has signed the extension study informed consent form and has completed all Month 18 visit assessments for Study CFD4870g or completed all Week 24 assessments for Study GX29455, he or she will be offered the opportunity to enroll in this extension study on the same day (Day 1) if they satisfy all eligibility criteria. The patient's study CFD4870g Month 18 visit assessments or Study GX29455 Week 24 visit assessment will be utilized for a patient's eligibility to enter this study. If applicable as per investigator discretion, the patient will confirm administration of antimicrobials prior to the Day 1 visit.

Please see the Study Flowchart provided in [Appendix 1-A](#) (for patients from Study CFD4870g) and [Appendix 1-D](#) (for patients from Study GX29455) for the schedule of screening and pretreatment assessments on the Day 1 visit.

4.6.3 Assessments during Treatment

After a patient has signed the informed consent form, the site will contact the IxRS to obtain a patient enrollment ID number assignment and to report the study drug distribution on the Day 1 visit (at conclusion of Month 18 visit in study CFD4870g or Week 24 visit in study GX29455). Patient self-administered antimicrobials in the pre- and post-injection period may be used at the investigator's discretion.

At all study visits the procedures and assessments should be performed prior to study drug administration unless otherwise indicated. All study visit assessments must be performed on the same day. *Note: see Section 3.1.3 for exception regarding delayed study treatment administration.*

The study scheduled visits should occur every 30 (± 7) days relative to the Day 1 visit date. Dosing should not occur earlier than 23 days after the previous dosing.

Please see the Study Flowcharts provided in [Appendix 1-A](#) through [Appendix 1-E](#) for the schedule of treatment period assessments.

4.6.4 Study Completion/Early Termination Visit

For patients who withdraw early from the study (prior to the Month 96 visit for patients enrolled from CFD4870g and prior to the Month 54 visit for patients enrolled from GX29455) for any reason, these patients should complete the ET visit assessments ≥ 30 days following the last study treatment. Patients who discontinue from the study will not be allowed to re-enter the study. Please see the Study Flowcharts provided in [Appendix 1-A](#) through [Appendix 1-E](#) for the assessments to be performed at the study ET visit.

4.6.5 Study Treatment Discontinuation/Early Termination Visit

Patients who prematurely discontinue the study treatment (prior to the Month 96 visit for patients enrolled from CFD4870g or prior to the Month 54 visit for patients enrolled from GX29455) will be also discontinued from the study, and they will be asked to return for an ET evaluation ≥ 30 days following their last study drug treatment for monitoring of adverse events and the study ET visit assessments.

Please see the Study Flowcharts provided in [Appendix 1-A](#) through [Appendix 1-E](#) for the assessments to be performed at the ET visit.

4.6.6 Unscheduled Safety Assessment Visit

If a patient experiences eye pain, a decrease in vision, unusual redness, or any other new ocular symptoms in the study eye, the investigator will determine whether the patient should return to the clinic for a safety assessment as soon as possible. If a visit is required, the assessments listed in [Appendix 1-F](#) will be performed.

4.7 PATIENT DISCONTINUATION

Patients have the right to voluntarily withdraw from the study at any time for any reason. In addition, the investigator has the right to withdraw a patient from the study at any time. Reasons for withdrawal from the study may include, but are not limited to, the following:

- Patient withdrawal of consent at any time
- Any medical condition that the investigator or Sponsor determines may jeopardize the patient's safety if he or she continues in the study
- Investigator or Sponsor determines it is in the best interest of the patient
- Patient non-compliance, defined as e.g., missed doses, visits

Every effort should be made to obtain information on patients who withdraw from the study. The primary reason for withdrawal from the study should be documented on the appropriate eCRF. However, patients will not be followed for any reason after consent has been withdrawn. Patients who withdraw from the study will not be replaced.

4.8 STUDY TREATMENT DISCONTINUATION

The investigator has the right to discontinue a patient from the study treatment for any medical condition that the investigator determines may jeopardize the patient's safety if he or she continues in the study treatment, for reasons of non-compliance (e.g., missed doses, visits), if the patient becomes pregnant, or if the investigator determines it is in the best interest of the patient. The reason for the treatment discontinuation should be recorded on the appropriate eCRF.

Treatment discontinued patients will be also discontinued from the study and will not be replaced or allowed to re-enter the study.

4.9 STUDY DISCONTINUATION

The Sponsor has the right to terminate this study at any time. Reasons for terminating the study may include, but are not limited to, the following:

- The incidence or severity of adverse events in this or other studies indicates a potential health hazard to patients
- Patient enrollment is unsatisfactory
- Data recording is inaccurate or incomplete

The Sponsor has the right to close a site at any time. Reasons for closing a site may include, but are not limited to, the following:

- Excessively slow recruitment
- Poor protocol adherence
- Inaccurate or incomplete data recording
- Non-compliance with the International Council for Harmonisation (ICH) guideline for Good Clinical Practice
- No study activity (i.e., all patients have completed the study and all obligations have been fulfilled)

4.10 POST-TRIAL ACCESS TO LAMPALIZUMAB

The Sponsor will offer post-study access to the study drug lampalizumab free of charge to eligible patients in accordance with the Roche Global Policy on Continued Access to IMPs as outlined below.

A patient will be eligible to receive study drug after the end of the study if all of the following conditions are met:

- The patient has a sight-threatening or severe medical condition and requires study drug treatment for his or her well-being
- There are no appropriate alternative treatments available to the patient
- The patient and his or her doctor comply with and satisfy any legal or regulatory requirements that apply to them

A patient will not be eligible to receive study drug after the end of the study if any of the following conditions are met:

- The study drug is commercially marketed in the patient's country and is reasonably accessible to the patient (e.g., is covered by the patient's insurance or would not otherwise create a financial hardship for the patient)
- The Sponsor has discontinued development of the study drug or data suggest that the study drug is not effective for GA
- The Sponsor has reasonable safety concerns regarding the study drug as treatment for GA
- Provision of study drug is not permitted under the laws and regulations of the patient's country

The Roche Global Policy on Continued Access to IMPs is available at the following Web site:

http://www.roche.com/policy_continued_access_to_investigational_medicines.pdf.

4.11 ASSAY METHODS

Drug concentration will be determined in serum using a validated ELISA method. ATA will be detected in serum using a validated ELISA.

4.12 STATISTICAL METHODS

4.12.1 Safety Analysis

Safety will be assessed by adverse events, clinical laboratory evaluations, and immunogenicity as measured by ATA. Safety analyses will include all patients who enrolled into the extension study and received at least one lampalizumab injection *in* the extension study. These patients will be grouped by the treatment received (*lampalizumab or sham*) when they were enrolled in the CFD4870 or GX29455 for safety analyses.

The primary safety analysis is planned to occur at the time when patients enrolled from Study CFD4870g have reached approximately 96 months follow-up and when patients enrolled from Study GX29455 have reached approximately 54 months follow-up.

The timing of the primary analysis may be adjusted according to the start of the open-label extension for Studies GX29176 and GX29185, to which patients from the extension study may have the opportunity to enroll. Earlier safety analyses of this study may be performed on an ad hoc basis.

All verbatim adverse event terms will be mapped to Medical Dictionary for Regulatory Activities (MedDRA) thesaurus terms, and adverse event severity will be graded according to an adverse event severity grading scale (see [Table 3](#)).

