3.1.3 All Extension Study Patients

A patient must satisfy all eligibility criteria at Day 1 visit and will be enrolled using an interactive response system (IxRS). All patients enrolled in the extension study will have the first ITV injection of lampalizumab administered by the investigator at the Day 1 visit (unless dose holding is medically justified by the investigator) which is scheduled on the same day and immediately following the conclusion of the Month 18 visit for Study CFD4870g or Week 24 visit for Study GX29455. Requisite Study CFD4870g Month 18 and Study GX29455 Week 24 assessment data will be extracted and incorporated into extension study Day 1 datasets.

All patients who enroll in Study GX28198 will have scheduled monthly visits with monthly study-drug treatment for the duration of their study participation (see [Table 1](#)).

Table 1 Dosing Schema

Treatment	Day 1 ^a	Monthly Lampalizumab Dosing Visit Month 1 through Visit Month 95 ^b or Visit Month 1 through Visit Month 53 ^c	ET ^e or Final visit Month 96 ^d or Month 54 ^d
Lampalizumab 10-mg ITV injections	x	x	

ET = early termination; ITV =intravitreal.

- ^a Day 1 visit will occur at the conclusion of the Month 18 visit for Study CFD4870g or Week 24 visit for Study GX29455; the first study drug administration for the extension study is at the Day 1 visit.
- ^b Patients enrolled from Study CFD4870g in the monthly treatment arm continue to receive monthly lampalizumab treatment (Months 1–95) without change; patients in the every-other-month treatment arm were crossed over to the monthly treatment arm and are receiving monthly lampalizumab treatment for the remainder of their 95-month study treatment period.
- ^c Patients enrolled from Study GX29455 will receive monthly treatment (visit Months 1–53) with lampalizumab irrespective of the treatment arm (Q2W or Q4W) they were randomized to in Study GX29455.
- ^d Month 96 visit is a final study visit for patients enrolled from Study CFD4870g and Month 54 visit is the final study visit for patients enrolled from Study GX29455; no study treatment will be administered at the final visit.
- ^e *Patients may undergo an ET visit as per protocol section 4.7 through 4.9; no study treatment will be administered at this visit.*

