The incidence and characteristics of adverse events, serious adverse events, and laboratory abnormalities will be assessed. At the time of study enrollment, if a patient has an ongoing adverse event from Study CFD4870g or Study GX29455, the event will be continuously followed in the extension study. Any new adverse events will be collected from the time of Day 1 visit (the first study drug administration) in the extension study until a patient completes the study or discontinues prematurely. Safety will be assessed on an ongoing basis using expeditious reporting of serious adverse events and adverse events of special interest. All adverse events *and pregnancies* will be recorded for the duration of this study.

Periodic review of safety will be performed by an internal Genentech Safety Review Committee, composed of the Medical Monitor, Drug Safety Scientist, and Biostatistician. External experts may be consulted.

Starting with the Day 1 visit, all patients will be contacted by study site personnel 7 (± 2) days after each injection to elicit reports of any decrease in vision, eye pain, unusual redness, or any other new ocular symptoms in the study eye. Patient-administered antimicrobials in the pre- and post-injection period may be used at the investigator's discretion.

Patients will be instructed to contact the investigator at any time if they have health-related concerns. If warranted, patients will be asked to return to the clinic as soon as possible for an unscheduled safety assessment visit ([Appendix 1-F](#)).

A finger-counting test will be conducted for each patient within 15 minutes following study treatment by the investigator; hand motion or light perception will be tested when necessary. IOP will be measured bilaterally prior to study treatment and at 60 (± 10) minutes after study treatment for the study eye only. If there are no safety concerns at 60 (± 10) minutes post treatment, the patient will be discharged from the clinic. If the IOP is increased by ≥ 10 mmHg from the pre-injection measurement at 60 (± 10) minutes the patient will remain in the clinic and will be treated according to the investigator's clinical judgment prior to the patient's discharge; if applicable, an Adverse Event eCRF page will be completed (see Section [5.3.5](#)).

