Detailed ocular examinations, including indirect ophthalmoscopy and slit-lamp examination, will be performed throughout the study. Routine hematology, serum chemistry, coagulation, and urinalysis profiles, as well as blood samples for antibodies to lampalizumab, will be obtained from all patients (see [Appendix 1-A](#) through [Appendix 1-E](#)).

The VA examiner will be masked to the patient's treated (study) eye and will perform only the VA (including refraction). The VA examiner is not allowed to perform any other tasks involving direct patient care.

Patients who are prematurely discontinued from the study treatment (prior to the Month 96 visit for CFD4870g patients and prior to the Month 54 visit for GX29455 patients) will be also discontinued from the extension study and will be asked to return for an ET evaluation ≥ 30 days following their last study drug treatment for monitoring of adverse events and the early study termination visit assessments (see [Appendix 1-A](#) through [Appendix 1-E](#)).

Serious adverse events will be collected and reported in compliance with Good Clinical Practice guidelines.

See Section [4.8](#) for dose-holding and study discontinuation criteria for adverse events.

If a patient's eye is injected with ranibizumab, the same post-dose safety assessments (finger counting, IOP measurement, and follow-up call) should be followed as for the study treatment. Treatment (dose) holding and/or treatment discontinuation for adverse events will be determined using the criteria in [Table 2](#) in Section [4.3.1.2](#). Associated adverse events should be recorded on the Adverse Event eCRF.

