5. ASSESSMENT OF SAFETY

5.1 SAFETY PARAMETERS AND DEFINITIONS

Safety assessments will consist of monitoring and recording adverse events, including serious adverse events and adverse events of special interest, performing protocol-specified safety laboratory assessments, measuring protocol-specified vital signs, and conducting other protocol-specified tests that are deemed critical to the safety evaluation of the study.

Certain types of adverse events require immediate reporting to the Sponsor, as outlined in Section [5.2](#).

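### As the visible schedules read, completers have no scheduled post-baseline central laboratory panel, so the laboratory part of the Section 4.12.1 safety assessment cannot describe them

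*Combined protocol and SAP*

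**What the plan says.** Section 4.12.1 rests the safety analysis on three kinds of data: "Safety will be assessed by adverse events, clinical laboratory evaluations, and immunogenicity as measured by ATA". The analysis population is every enrolled patient with at least one injection in the extension. The primary analysis is planned for about Month 96 for patients from Study CFD4870g and about Month 54 for those from Study GX29455.

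Section 3.5 supports this twice: "The incidence and characteristics of adverse events, serious adverse events, and laboratory abnormalities will be assessed", and "Routine hematology, serum chemistry, coagulation, and urinalysis profiles, as well as blood samples for antibodies to lampalizumab, will be obtained from all patients". The second sentence refers to Appendices 1-A to 1-E for timing. Section 5.1 counts among the safety assessments "performing protocol-specified safety laboratory assessments, measuring protocol-specified vital signs".

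The schedules mark the central laboratory row at Day 1 (extracted from the parent study) and at ET in 1-A and 1-D, and at ET alone in 1-B, 1-C and 1-E. Month 96 in 1-C and Month 54 in 1-E are blank.

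ET belongs to early exit. Section 4.6.4 says of patients who withdraw early that "for any reason, these patients should complete the ET visit assessments". Section 4.6.5 says of patients who stop study treatment early that "they will be asked to return for an ET evaluation". Table 1, footnote e, adds: "Patients may undergo an ET visit as per protocol section 4.7 through 4.9". Section 4.9 is the one in which "The Sponsor has the right to terminate this study at any time".

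**The concern.** The primary objective covers long-term systemic as well as ocular safety, and laboratory values are one of the three named bases for judging it. If the schedules are followed as they read, the laboratory summary holds a baseline value for everyone and a later scheduled value only for patients who leave early. Section 4.12.4 rules out imputation for the safety analysis, so completers would contribute baseline values only. These are the patients with the longest follow-up, and the study would have no scheduled laboratory data on them after Day 1. Any statement about laboratory safety over 96 or 54 months would in fact describe a group selected by early exit.

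**Working it through.** The plan states no figure to reproduce. The check reads the schedule rows against their visit headings and then looks for text that fills the gap.

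**Step 1. Marks in the schedules.** ATA is the anti-therapeutic antibody sample.

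| Schedule | Central laboratory panel | ATA serum |
|---|---|---|
| 1-A (Day 1, Months 1–30) | Day 1 (extracted), ET | Day 1 (extracted), Months 6, 12, 24, ET |
| 1-B (Months 31–66) | ET | Months 36, 42, marks under 49–53 and 61–65, ET |
| 1-C (Months 67–96) | ET | Month 96, ET |
| 1-D (Day 1, Months 1–24) | Day 1 (extracted), ET | Day 1 (extracted), Months 6, 12, 24, ET |
| 1-E (Months 25–54) | ET | Month 54, ET |

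**Step 2. Scheduled post-baseline samples for a completer** (marks after Day 1, excluding ET).

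- CFD4870g, schedules 1-A + 1-B + 1-C, 30 + 36 + 30 = 96 visits. Panels: 0 + 0 + 0 = 0. ATA: 3 + 4 + 1 = 8, approximate because two marks in 1-B look shifted.
- GX29455, schedules 1-D + 1-E, 24 + 30 = 54 visits. Panels: 0 + 0 = 0. ATA: 3 + 1 = 4.

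**Step 3. Does other text supply a panel?**

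- Sections 3.5 and 4.6.1.4 send the reader back to the same appendices.
- Section 4.6.4 has study completion in its heading but assigns assessments only to early withdrawals. Section 4.6.5 covers early treatment discontinuation. Footnote b of each schedule covers early withdrawal.
- Appendix 1-F (unscheduled visit) lists no laboratory samples.
- Appendix 9 names the Laboratory Manual as a further source of timepoints. The manual is not in the documents, so this remains open.

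**Step 4. Could the blanks come from damaged tables?** In the last two columns of 1-C and of 1-E, leaving out rows tied to an injection and counting SD-OCT from its text, 17 rows carry a mark.

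| | Both | Final visit only | ET only | Total |
|---|---|---|---|---|
| 1-C | 9 | 5 | 3 | 17 |
| 1-E | 9 | 5 | 3 | 17 |

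The three ET-only rows in each table are the laboratory panel, vital signs and physical examination. All the other rows are marked at the final visit: 14 + 14 = 28 of 28. The other blanks in these columns, 5 + 5 = 10, are all at ET. Some of those look wrong: the IxRS cell is blank at ET, although the footnote requires contact then. The visible damage in these columns is therefore at ET, not at the final visit.

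The ATA row in both tables has separate marks at the final visit and at ET, so the two columns can be told apart. The laboratory row has as many cells as its header in all five schedules (14, 13, 11, 12 and 11). That match does not hold on every page: a continuation page of 1-B has 14 cells under 13 headings, and the last page of 1-D has lost Month 24.

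**Step 5. Bound for misplaced marks.** If the laboratory mark in 1-C and 1-E belonged one column to the left, a completer would have 1 panel, at the final visit. If that held in every schedule, the count would be 3 (Months 30, 66, 96) or 2 (Months 24, 54).

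**The case against.** Four arguments go the other way.

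*The documents are incomplete and the tables are damaged.* The Laboratory Manual may hold timepoints, and parts of the same tables are plainly altered. This stands as a limit on certainty. The claim is about the visible schedules, and checking the source comes first. It does not reverse the reading, because the laboratory pattern is the same in all five schedules.

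*The blank may be a drafting slip.* Table 1 puts ET and the final visit in one column, and the heading of Section 4.6.4 joins completion with early termination. That is plausible, but neither place assigns laboratory samples to completers. If it is a slip, marking the cells corrects it.

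*Sparse laboratory testing may be deliberate.* The primary outcome is adverse events, laboratory values are not listed among the outcome measures, Section 3.5 expects low systemic levels, and Section 5.3.5.4 turns qualifying abnormalities into adverse events. This is a legitimate choice. It is at odds with naming laboratory evaluations as a basis of safety without saying whom they can describe.

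*Many patients may have an ET panel after all.* Sponsor termination under Section 4.9 could lead to ET visits. So could moving to the other open-label extension mentioned in Section 4.12.1, because Section 4.6.4 covers early withdrawal for whatever reason. Either would narrow the gap. The documents do not say how many patients would take these routes.

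A reader might also infer that ET values are uninformative because they are taken at least 30 days after the last injection. The documents do not support that as a contrast: no drug is given at the final visit (Table 1, footnote d) and visits are every 30 (±7) days, so a completer's final visit has about the same timing.

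**Conclusion.** The point holds for the central laboratory panel: 0 scheduled post-baseline panels for a completer over 96 or 54 visits, as the visible schedules read. It assumes that the blank final-visit cells are blank in the source tables, that the Laboratory Manual adds no timepoints, and that ET assessments are not applied to completers. Scheduled post-baseline values would then come only from patients who leave early, by withdrawal, treatment discontinuation, Sponsor termination or rollover. The laboratory part of the Section 4.12.1 assessment could not describe completers. It should be fixed; confidence is medium because of the tables and the unseen manual.

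Three stronger conclusions are tempting and not supported.

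- A reader might infer that Section 3.5 is contradicted. It is not, word for word, since every patient has a Day 1 panel.
- A reader might infer that the safety conclusion as a whole fails. The adverse-event primary outcome and ATA collection are unaffected.
- A reader might give vital signs and physical examination equal weight, since their rows show the same pattern. Section 4.12.1 names neither, and Appendix 1-F lists both, so they are a secondary point of consistency with Section 5.1.

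**What to change.** 1. Check the final-visit and ET columns of Appendices 1-C and 1-E against the source tables, and check the Laboratory Manual for timepoints.
2. If the cells are blank and the manual adds nothing, mark the central laboratory panel at Month 96 (1-C) and Month 54 (1-E). ATA blood is already drawn at both visits. When doing so, decide whether vital signs and physical examination should be marked there too.
3. In Section 4.12.1, require the number of patients with a post-baseline value beside each laboratory summary, split by completer and ET.
4. If no samples are added, say in Sections 3.5 and 4.12.1 that scheduled post-baseline laboratory data come only from ET visits and do not support a laboratory-safety conclusion for completers.

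Cost: one laboratory cell in each of two tables, one sentence in Section 4.12.1, and a few extra tubes per completer at an existing visit. The alternative in item 4 costs wording only, but gives up the laboratory conclusion for completers.
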